7.1 Follow-up of Patients after End of Study Treatment

For all patients who were included into this trial, whether discontinued treatment prematurely or completed the entire study, the final examination will be performed 18 months after transplantation (Visit 7 and / or visit 7.1, Month 18).

At a minimum, all patients who discontinue from the study treatment prematurely will be contacted within 30 days following study treatment termination, to follow-up on any safety issues. Documentation of MACE, infections, immunosuppressive medication, and other concomitant medication should be continued for the period of 30 days following the last dose of the per protocol immunosuppressive regimen.

For all patients documentation of SAEs should be continued until 30 days after the patient has stopped study participation (visit 7 or 7.1, Month 18). Any SAEs experienced after this 30 days period should only be reported to Novartis if the investigator suspects a causal relationship to the study drug.

Following discontinuation of the per protocol immunosuppressive regimen, the immunosuppressive therapy will be on the investigator's discretion.

7.2 Information to be collected on Screening failures

If a patient who signed informed consent fails to be **enrolled** into the trial at Month 3 for any reason, the patient's number and the reason for non-enrollment will be entered into the Screening Failure Log.

7.3 Patient demographics / other baseline characteristics

The following demographic data and other baseline characteristics will be recorded:

- **Demography:** date of birth, sex, and ethnic origin
- **Relevant medical history / current medical conditions:**

Relevant prior diseases and surgeries as well as concomitant diseases will be recorded with date of diagnosis / surgery and information on whether it is an active problem.

For women of childbearing potential the serum pregnancy test (β -HCG) will be performed locally within 7 days prior to Screening (Month 3 post Tx). Results must be available and negative prior to administration of medication and reported on the CRF.

- **Renal history**

Any significant prior and current renal diseases (e.g. presence of glomerulonephritis, nephrectomia, etc.) will be recorded with date of diagnosis and information whether it is an active problem).

- **Transplantation information:**

Donor information

age, sex, race, viral serology on CMV, EBV, HepC, HbsAg, HIV

Recipient information

date of transplantation, duration of cold ischemia time, percentage of panel reactive antibodies (PRA) , viral serology on CMV, EBV, HepC, HbsAg, HIV, end stage disease leading to transplantation

Initiated immunosuppressive regimen, including induction therapy

7.4 Treatments

Records of all immunosuppressive drugs (Everolimus, Cyclosporin A, Tacrolimus, MPA, corticosteroids) used and dosages administered are to be kept during the whole study. Starting 5 days prior to the Screening visit, all changes to the medication dosing regimen should be recorded in the Dosage Administration Record CRF, along with the reason for change and dates.

The immunosuppressive regimen initiated after transplantation, including information whether and which induction therapy was applied, will be recorded.

Drug accountability for **Everolimus** medication will be noted by the investigator and/or study personnel at each visit using pill counts. This information should be captured in the source document at each visit.

7.5 Efficacy

The following efficacy variables will be obtained and recorded:

- **Endomyocardial biopsy – Rejection episodes / graft loss / re-transplant**

Per protocol biopsies will be performed at visits 2, 4, 6 and 7 and results of a biopsy that may have been performed at Month 1 post Tx will be recorded retrospectively. Additionally, a biopsy will be performed in any case of suspected rejection. Biopsies will be read and interpreted by local pathologists according to the ISHLT 1990 and/or 2004 diagnosis criteria ([Stewart et al, 2005](#)). A copy of the pathology report will be collected and filed in the investigator's folder. The results will be recorded on the Endomyocardial Biopsy CRF at respective visit.

All suspected rejection episodes must be recorded on the Endomyocardial Biopsy log / Suspected Rejection CRF, with the date rejection was first suspected, whether anti-rejection therapy was administered, whether the acute rejection was confirmed or with final clinical diagnosis specified, and final clinical outcome.

Biopsy-proven acute rejection

(ISHLT 1990 grade \geq 3A resp. ISHLT 2004 grade \geq 2R)

The occurrence of a biopsy-proven acute rejection is diagnosed from per-protocol biopsies or from biopsies performed for suspected rejection episodes. Per protocol biopsies will be performed at Visits 2, 4, 6 and 7 / 7.1.

In all suspected rejection episodes, a graft core biopsy and an echocardiography will be performed within 48 hours, regardless of the initiation of anti-rejection therapy. The results including date of occurrence of first symptoms will be recorded in the Endomyocardial Biopsy log / Suspected Rejection CRF and will be used for the efficacy analysis.

Rejection episodes will be reported on the Endomyocardial Biopsy log / Suspected Rejection CRF only, and not on the AE CRF. An Endomyocardial Biopsy log / Suspected Rejection CRF will be completed each time a suspected or biopsy-proven acute rejection has occurred. Rejection episodes occurring more than 10 days after the start of the preceding one will be considered as a new rejection episode.

Rejection with hemodynamic compromise

The occurrence of an acute rejection with hemodynamic compromise will be assessed using the Hemodynamic Compromise CRF. Positive inotrope therapy or vasoactive treatment will be recorded on the Prior-/Concomitant medications CRF.

Graft loss / re-transplantation

The allograft will be presumed to be lost on the day the patient is scheduled for re-transplantation. This will be reported on the End of Treatment CRF if medication is discontinued prematurely and Study Completion CRF. Graft loss / re-transplantation are considered a Serious Adverse Event and must be reported on the Serious Adverse Event Case Report Form, which must be faxed to Novartis.

Major Adverse Cardiac Events (MACE)

Major Adverse Cardiac Event will be defined as one of the following:

- any death
- myocardial infarction
- coronary artery bypass grafting

All major adverse cardiac events will be recorded on the CRF and are subject to expedited reporting as specified in [section 8.1](#).

- **Echocardiogram**

Echocardiograms will be performed as needed for suspected rejection episodes. Results will be recorded on the Echocardiogram CRF.

- **Electrocardiograms (ECG)**

A 12-lead ECG will be written and documented in the CRF with ventricular rate, PQ interval, QRS duration and QT interval.

Additionally, the investigator will assess the following:

heart rate: normal, bradycard, tachycard,
rhythm: eurhythmia, arrhythmia,
block signs: S-A Block,
 AV-Block °I, °II (Wenckebach, Mobitz, Periodic), or °III,
 Interventricular Block (right bundle-branch, left bundle-branch)

7.6 Safety

Safety assessments will consist of monitoring and recording all infections, AEs and SAEs, the regular monitoring of hematology, blood chemistry, and regular measurement of vital signs.

Infections

All infection episodes must be recorded on the Infection CRF (CMV infections on the CMV Infection CRF); they should not be collected on the AE CRF. Infections should be listed with severity, relationships, sample site, genus and species of microorganism specified, start and end dates, action taken.

CMV infection is defined as seroconversion of a negative patient or isolation of CMV from urine, saliva, blood or any other tissue. Symptomatic or clinically apparent CMV infection should be classified according to the criteria of the Paris CMV workshop (1993) into presumptive and proven CMV disease. Briefly, the diagnosis of presumptive CMV disease requires the demonstration of CMV viremia by any method in addition to fever $> 38^{\circ}\text{C}$ for at least 2 days in the absence of another clinical source, combined with one of the following findings: atypical lymphocytosis $> 3\%$, WBC count $< 4,000/\text{mm}^3$ or platelet count $< 100,000/\text{mm}^3$. The diagnosis of proven CMV disease requires, apart from the presence of signs and/or symptoms of organ involvement, the detection of CMV in the affected organ. Particular attention will be given to clinically apparent CMV infections (presumptive and proven CMV disease).

Adverse events

An adverse event is the appearance or worsening of any undesirable sign, symptom, or medical condition occurring after starting the study drug even if the event is not considered to be related to study drug. Study drug includes the investigational drug under evaluation and the comparator drug or placebo that is given during any phase of the trial. Medical conditions / diseases present before starting study drug are only considered adverse events if they worsen after starting study drug. Abnormal laboratory values or test results constitute adverse events only if they induce clinical signs or symptoms, are considered clinically significant, or require therapy.

The occurrence of adverse events should be sought by non-directive questioning of the patient at each visit during the study. Adverse events also may be detected when they are volunteered by the patient during or between visits or through physical examination, laboratory test, or other assessments. As far as possible, each adverse event should be evaluated to determine:

1. the severity grade (mild, moderate, severe)
2. its relationship to the study drug (Everolimus) (suspected/not suspected)
3. its duration (start and end dates or if continuing at final exam)
4. action taken i.e:
 - (a) no action taken;
 - (b) study drug dosage adjusted/temporarily interrupted;
 - (c) study drug permanently discontinued due to this adverse event;
 - (d) concomitant medication taken;
 - (e) non-drug therapy given;
 - (f) hospitalization/prolonged hospitalization
5. whether it is serious, where a serious adverse event (SAE) is defined as one which:
 - is fatal or life-threatening
 - results in persistent or significant disability/incapacity
 - constitutes a congenital anomaly/birth defect
 - requires inpatient hospitalization or prolongation of existing hospitalization, unless hospitalization is for:

- routine treatment or monitoring of the studied indication, not associated with any deterioration in condition
- elective or pre-planned treatment for a pre-existing condition that is unrelated to the indication under study and has not worsened since the start of study drug
- treatment on an emergency outpatient basis for an event not fulfilling any of the definitions of a SAE given above and not resulting in hospital admission
- social reasons and respite care in the absence of any deterioration in the patient's general condition
- treatment of acute rejection; acute rejections are considered to be a protocol exempted event. They should not be reported simply because they result in a hospitalization and thus meet the criteria for an SAE.. Acute rejections should be reported as SAEs only if they are unusual in appearance, clinical course and/or are graft threatening
- is medically significant, i.e., defined as an event that jeopardizes the patient or may require medical or surgical intervention to prevent one of the outcomes listed above
- is a MACE or a graft loss

Unlike routine safety assessments, SAEs are monitored continuously and have special reporting requirements; see [Section 8.1](#).

All adverse events should be treated appropriately. Such treatment may include changes in study drug treatment including possible interruption or discontinuation, starting or stopping concomitant treatments, changes in the frequency or nature of assessments, hospitalization, or any other medically required intervention. Once an adverse event is detected, it should be followed until its resolution, and assessment should be made at each visit (or more frequently, if necessary) of any changes in severity, the suspected relationship to the study drug, the interventions required to treat it, and the outcome.

Information about common side effects already known about the investigational drug can be found in the Investigator Brochure or will be communicated between IB updates in the form of Investigator Notifications. This information will be included in the patient informed consent and should be discussed with the patient during the study as needed.

Physical examination

Information about the physical examination must be present in the source documentation at the study site. Significant findings that are present prior to study enrollment must be included in the Relevant Medical History / Current Medical Conditions CRF. Significant findings made after the start of the study which meet the definition of an AE must be recorded on the AE CRF.

Vital signs

Height will be recorded at Screening visit (Visit 1) only. Vital signs will be recorded at every study visit, and include body temperature, radial pulse rate, systolic and diastolic blood pressure and weight (kg). Blood pressure and pulse rate will be assessed after the patient has rested in the sitting position for at least five minutes; blood pressure should be assessed at the same arm each time of determination.

Laboratory evaluations

The center's local laboratory will be used to analyze the clinical laboratory data during the study.

The following variables will be examined:

Hematology: hemoglobin, leukocytes (including differential blood count and absolute neutrophil count), red blood cell and platelet count hematokrit (HK)

Blood chemistry: sodium, potassium, urea, creatinine, glucose (fasting) uric acid, ALAT, ASAT, albumin, total bilirubin, total cholesterol, HDL, LDL, triglycerides, CPK

Viral Serology: CMV (including pp65 Ag)
only at Screening (or up to 6 months prior screening):
EBV, Hepatitis B (HBsAg), Hepatitis C, HIV

Frozen Storage: 2 tubes of EDTA blood

Urinanlysis: protein
GFR will be calculated according to the formula given below,
[Section 7.7](#)

For determination of the drug levels see [Section 7.10](#).

Viral serology

All patients should be tested for EBV, Hepatitis B (HBsAg), Hepatitis C, CMV and HIV prior to study inclusion (earlier tests \leq 6 months are acceptable). Any patients with a positive Hepatitis B surface antigen or Hepatitis C or HIV will be excluded from study participation. If results are not available at the Screening visit, the patient may be included. If results of a newly initiated assessment at the Screening visit will be positive, the patient will subsequently be dropped from the study and administered the standard care provided by the center.

During the course of the trial, only CMV status (including pp65 Ag) will be assessed.

7.7 Tolerability

Renal safety and tolerability will be the main objective of this trial. The following variables of renal safety and tolerability will be obtained and recorded:

- **Glomerular Filtration Rate (GFR)**

The glomerular filtration rate (GFR) is the best clinical estimate of renal function in health and disease, and correlates well with the clinical severity of renal function disturbances. Several studies have shown that in patients with progressive renal disease, GFR declines or reciprocal serum creatinine levels elevates linearly over time in a predictable manner.

The GFR will be calculated via MDRD (primary endpoint) and Cockcroft-Gault-Formula:

Calculated value of GFR in ml / min - **MDRD formula**

For men: $GFR = 170 \times (\text{serum creatinine}^{-0,999}) \times (\text{age}^{-0,176}) \times (\text{urea nitrogen}^{-0,17}) \times (\text{albumin}^{0,318})$

For women: $GFR = 170 \times (\text{serum creatinine}^{-0,999}) \times (\text{age}^{-0,176}) \times (\text{urea nitrogen}^{-0,17}) \times (\text{albumin}^{0,318}) \times 0.762$

with urea nitrogen = urea / 2.144.

Calculated value of GFR in ml/min - **Cockcroft-Gault formula**

For men: $GFR = \frac{(140 - \text{Age}) \times \text{Body Weight} [\text{kg}]}{72 \times \text{Serum Creatinine} [\text{mg/dl}]}$

For women: $GFR = \frac{0,85 \times (140 - \text{Age}) \times \text{Body Weight} [\text{kg}]}{72 \times \text{Serum Creatinine} [\text{mg/dl}]}$

units: [g/dl] for albumin, [mg/dl] for serum creatinine, [mg/dl] for serum urea

Furthermore, tolerability of study medication can be assessed from the rate of patients who withdraw prematurely from study medication or in whom study medication had to be converted to another immunosuppressive regimen due to abnormal laboratory results, adverse events, or toxicity.

All changes to the immunosuppressive medication dosing regimen will be recorded on the Dosage Administration Record CRF, along with the reason for change.

- **Serum Creatinine**

For the analysis of serum creatinine, venous blood will be drawn and analyzed in the center's local laboratory.

Besides changes from baseline, the slope of the decline in reciprocal serum creatinine (1 divided by serum creatinine) versus time will be analyzed as an indicator of progressive renal disease (for the creatinine slope, see [Gretz 1994](#); [Lacour 1992](#); [Kaplan et al., 2003](#); [Kasiske et al., 2001](#)).

7.8 Resource utilization

Approximately 95% of treatment costs of transplanted patients are related to hospitalization, immunosuppressants and concomitant medication. As information on immunosuppressants, concomitant medication and dialysis is collected traditionally in all transplant clinical studies, the focus of additional resource utilization data collection should be on hospitalization events. Thus, all relevant information about initial hospitalization due to transplantation and hospitalization after transplantation (in the transplant center and outside) will be recorded. The information collected this way includes reason for admission (including admission for adverse events, including infection, for dialysis post transplantation, and for treatment of acute rejection), the dates of admission and discharge, number of days on Intensive Care Units and number of days on a normal ward.

7.9 Health-related Quality of Life

None

7.10 Pharmacokinetics

The actual sample collection times, and the date and time of the previous drug dose (Everolimus, Tacrolimus or Cyclosporin A) will be recorded on CRF using a 24 hour clock.

Cyclosporin/Tacrolimus A whole blood levels will be measured starting at Screening Visit. For patients of the CNI group Cyclosporin A/Tacrolimus blood level will be measured at every study visit, for patients of the CNI-free group Cyclosporin A/Tacrolimus blood level will be measured until Cyclosporin A or Tacrolimus is removed from the immunosuppressive regimen (Month 6 or 8 post Tx).

Everolimus blood levels will be measured in all patients starting at Screening Visit and at every study visit thereafter (if applicable).

- **Cyclosporin A (CsA) whole blood tests**

Analysis of the Cyclosporin A whole blood levels will be performed locally at the center. Whole blood level for CsA will be assessed within 5 minutes before the Cyclosporin A administration (C0-h level).

- **Tacrolimus (Tac) whole blood tests**

Analysis of the Tacrolimus whole blood levels will be performed locally at the center. Whole blood level for Tac will be assessed 5 minutes before the Tacrolimus administration (C0-h level).

- **Everolimus whole blood tests**

For the analysis of the Everolimus whole blood levels 2 ml of blood should be

drawn in EDTA tubes. The C-0h level will be obtained with blood sampling within 5 minutes prior to medication intake.

7.11 Pharmacogenetics/pharmacogenomics

None.

7.12 Other biomarkers

None.

7.13 Additional Assessments

None

8 Safety monitoring

8.1 Serious adverse event reporting

To ensure patient safety, every SAE, regardless of suspected causality, occurring after the patient has signed the informed consent form and until 30 days after the patient has stopped **study participation** must be reported to Novartis within 24 hours of learning of its occurrence.

Any SAEs experienced after this 30 days period should only be reported to Novartis if the investigator suspects a causal relationship to the study drug. Recurrent episodes, complications, or progression of the initial SAE must be reported as follow-up to the original episode within 24 hours of the investigator receiving the follow-up information. An SAE occurring at a different time interval or otherwise considered completely unrelated to a previously reported one should be reported separately as a new event.

Information about all SAEs is collected and recorded on the Serious Adverse Event Report Form. The investigator must assess the relationship to study drug, complete the SAE Report Form in English, and send the completed, signed form by fax within 24 hours to the local Novartis [REDACTED]

[REDACTED]

[REDACTED]

[REDACTED]

[REDACTED]

[REDACTED]

8.2 Pregnancies

To ensure patient safety, each pregnancy in a patient on study drug must be reported to Novartis within 24 hours of learning of its occurrence. The pregnancy should be followed up to determine outcome, including spontaneous or voluntary termination, details of the birth, and the presence or absence of any birth defects, congenital abnormalities, or maternal and/or newborn complications.

Pregnancy should be recorded on a Clinical Trial Pregnancy Form and reported by the investigator to the local Novartis [REDACTED]

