In cases of recurrent infections serum antibody concentration should be measured; if hypogammaglobulinemia presents as persistent and clinically significant, patients should be examined accurately and appropriate actions should be taken; dose reduction or change of immunosuppression should be taken into consideration.

Patients with recurrent pulmonary disorders e.g. cough/dyspnea should as soon as possible be examined accurately for signs of bronchiectasis; dose reduction or change of immunosuppression should be taken into consideration.

Corticosteroids must be added to the immunosuppressive regimen in all patients, according to local standard. A dose of 0.05 – 0.3 mg/kg prednisolone or equivalent should be continued throughout the whole study.

Safety recommendations regarding the use of MPA:

MPA is a powerful human teratogen, which increases the risk of spontaneous abortions and congenital malformations in case of exposure during pregnancy. Therefore following safety recommendations should be followed for all patients that are receiving MPA (f.ex. CellCept or myfortic).

Investigators should ensure that women and men that are receiving MPA understand the risk of harm to the baby, the need for effective contraception, and the need to immediately consult responsible investigator if there is a possibility of pregnancy or a suspected gap of contraception. In addition, patients should not donate blood during therapy or for at least 6 weeks following discontinuation of MPA.

Recommendations for female patients:

Before starting treatment with MPA, women of child bearing potential must have undergone pregnancy testing, i.e. done at Screening, Baseline, Switch and following study visits (Assessment Schedule Table 7-1) in order to exclude unintended exposure of the embryo to mycophenolate. A pregnancy β -HCG test is mandatory for all female patients in this trial at all indicated visits (Table 7-1).

Pregnancy tests should be repeated as clinically required (e.g. after any gap in contraception is reported). Results of all pregnancy tests should be discussed with the patient.

Women of childbearing potential should use two reliable forms of contraception simultaneously before starting therapy, during therapy, and for six weeks after stopping treatment with MPA.

Recommendations for male patients

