Sexually active men (including vasectomized men) are recommended to use condoms during treatment and for at least 90 days after cessation of treatment. In addition, female partners of male patients treated with MPA are recommended to use highly effective contraception during treatment and for a total of 90 days after the last dose.

Men should not donate semen during therapy with MPA or for 90 days following discontinuation of MPA.

Table 6-1 Schematic diagram of medication administration

Phase	No Study	Prephase	Study Drug Treatment						
			Run In	BL	Switch	Maintenance			
Visit		1	2	3	4	5	6	7	
Month post Tx	0 - 3	3	6	8	9	10	12	18	
Randomization			X						

Treatments				
CNI group				
- Everolimus		center practice	C0-h level: 5 – 10 ng/mL	
- CNI (Cyclosporin A/ Tacrolimus)		acc. to blood level *	acc. to blood level *	acc. to blood level *
- MPA		center practice	none	None
- Steroids		0.05 – 0.3 mg/kg	0.05 – 0.3 mg/kg Prednisolone or equivalent	
CNI-free group				
- Everolimus		center practice	C0-h level: 5 – 10 ng/mL	
- CNI (Cyclosporin A/Tacrolimus)		acc. to blood level *	CyA: C0 level of ≤ 75 ng/mL for 8 weeks, then removal Tac: C0 level of ≤ 5 ng/mL for 8 weeks, then removal	None

- MPA		center practice	MMF 1.5 – 3 g/d OR EC-MPS 1440 – 2880 mg/d	MMF 1.5 – 3 g/d OR EC-MPS 1440 – 2880 mg/d
- Steroids		0.05 – 0.3 mg/kg	0.05 – 0.3 mg/kg Prednisolone or equivalent	

BL

= Baseline visit: day of randomization – Month 6 post Tx

CNI Group: treatment post randomization: Everolimus + Cyclosporin A/Tacrolimus + corticosteroids

Cyclosporin A Dosage: Month 1 - 6: C0-h levels 100 – 200 ng/mL
Month >6: C0-h levels 50 – 150 ng/mL
(cf. section 6.5.2)

Tacrolimus Dosage: Month 1 - 6: C0-h levels 5 - 10 ng/mL
Month >6: C0-h levels 3 - 8 ng/mL

CNI-free Group: treatment post randomization: Everolimus + MPA + corticosteroids

Cyclosporin A Dosage: Month 1 - 6: C0-h levels 100 – 200 ng/mL
Month 6 - 9: C0-h levels ≤75 ng/mL
(cf. section 6.5.2)

Tacrolimus Dosage: Month 1 - 6: C0-h levels 5-10 ng/mL
Month 6 - 9: C0-h levels ≤5 ng/mL

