10.4 Study treatments

10.4.1 Study medication

Study medication is Everolimus, RAD001); the other components of the immunosuppressive regimens are considered as concomitant medication.

Duration (days) of Everolimus, study medication application will be summarized. Dosage averages will be calculated including and excluding zero doses for periods of temporary interruption of study medication regardless of whether this was due to safety reasons or patients' non-compliance. Daily Everolimus, dose levels will be summarized with mean, standard deviation, minimum, median, and maximum by time interval. Frequency of dose reduction (including temporary dose interruption) for safety reasons as per protocol guidelines as well as average daily dose will be presented by visit. Reasons for dose adjustments (including temporary dose

interruption) will be presented by frequency distribution. Permanent treatment discontinuations will be analyzed by frequencies.

These analyses will be performed per treatment group, for the ITT- and the PP population and related to the study phases (see [section 10.1](#)).

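### Pregnancy reporting in section 8.2 stops with study drug and omits partners, although the protocol's own contraception periods run on after treatment and include partners

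*Protocol*

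**What the plan says.** Section 8.2 is the only readable rule on reporting pregnancies in either document: "each pregnancy in a patient on study drug must be reported to Novartis within 24 hours of learning of its occurrence". A reported pregnancy is then followed to its outcome, including the birth and any defect, with no time limit.

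Section 6.5.1 warns that MPA is strongly teratogenic in humans. It asks women of childbearing potential to use two methods of contraception "before starting therapy, during therapy, and for six weeks after stopping treatment with MPA". Sexually active men are advised to "use condoms during treatment and for at least 90 days after cessation of treatment", and their female partners are "recommended to use highly effective contraception during treatment and for a total of 90 days after the last dose". Inclusion criterion 5 gives women a different period, three months counted from stopping the study.

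The term study drug is not used in one sense:

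- Protocol section 10.4.1 names everolimus as study medication and says "the other components of the immunosuppressive regimens are considered as concomitant medication".
- Protocol section 7.6 first defines study drug to include the comparator, then asks for causality against study drug with everolimus in brackets.
- SAP section 2.1.1 counts cyclosporin A, tacrolimus and MPA as study drug too.

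Section 8.1 requires SAE reports from consent until 30 days after study participation ends. Later SAEs "should only be reported to Novartis if the investigator suspects a causal relationship to the study drug".

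**The concern.** The protocol names a fetal hazard, asks for precautions that continue after the last dose, and extends them to the partners of male patients. The reporting rule has neither feature: it is limited to patients, and to the time on study drug. The Amendment 4 rationale lists new MPA safety information for section 6.5.1 and extra pregnancy tests for section 7 and Table 7-1, but nothing for section 8.2.

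What is at stake is safety information. An exposed pregnancy that the site knows about might never reach the sponsor, and its outcome, normal or not, might not be recorded. Section 6.5.1 has men and women on MPA told to consult the investigator at once about a possible pregnancy, so a site may well hear of a case that it has no stated duty to pass on. After the switch, MPA belongs to the CNI-free regimen only, so the gap falls mainly on that arm.

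**Working it through.** No sample size, power or event figure underlies this point. The check sets the reporting rule beside the periods the protocol itself gives.

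**1. Lengths of the periods**

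- Section 8.2, after study drug ends: 0 days.
- Section 6.5.1, women after MPA: 6 × 7 = 42 days.
- Section 6.5.1, male patients and their partners after MPA: 90 days.
- Inclusion criterion 5, women: 3 months after stopping the study, about 3 × 365.25/12 = 91 days.
- Section 8.1, SAEs: 30 days after study participation ends.

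**2. Who is covered**

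| Case | Section 8.2 as written |
|---|---|
| Patient conceives while on everolimus | Reportable, followed to outcome |
| Patient has stopped MPA, continues everolimus, conceives | Reportable: everolimus is study drug under every definition |
| Patient is off everolimus, still on MPA, conceives | Unclear: depends on which definition is applied |
| Patient conceives after study treatment has ended, within the contraception periods | Not covered under any definition |
| Female partner of a male patient, at any time | Not covered under any definition |

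**3. Whether the fourth case can arise within the trial's own procedures**

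It can. Sections 6.5.5 and 7.1 keep patients in follow-up to Month 18 after they stop study drug. Table 7-1 schedules a β-HCG test in the column for Visits 7 and 7.1, and Visit 7.1 exists only for those who stopped early. A positive result there comes from a protocol test in a patient who is no longer on study drug.

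**4. Whether the SAE rule closes the gap**

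The SAE window is counted from the end of participation, so its length relative to the last dose varies.

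- If MPA stops when participation ends, the window is short by 42 − 30 = 12 days for women and by 90 − 30 = 60 days for the male and partner period.
- If a patient stops at Month 12 and stays in follow-up to Month 18, SAE reporting lasts 6 months + 30 days, about 7 months after the last dose, which exceeds both periods.
- The criterion 5 period is also counted from stopping the study, so there the shortfall is about 91 − 30 = 61 days whenever the drug stops.

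Length is not the main limitation. Section 7.6 makes a congenital anomaly an SAE, but not a pregnancy as such, and neither section 7.6 nor section 8.1 is written for partners.

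**The case against.** The strongest reply is that the gap is small and partly covered. Pregnancy and unwillingness to use contraception are exclusions, and two methods are required. Early discontinuers have a safety contact within 30 days and the Month 18 assessments twice. Patients on MPA are told to consult the investigator, and a birth defect is an SAE that remains reportable late if causality is suspected. All of this stands and limits the likely number of cases. None of it places a duty on the site to report a post-treatment pregnancy as such, or one in a partner.

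A reader might infer more than the documents support:

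- That a patient on MPA without everolimus is definitely unreportable. The definitions in protocol sections 7.6 and 10.4.1 and SAP section 2.1.1 conflict, so this is unsettled.
- That there is no cover after MPA for anyone. Patients who stop MPA but stay on everolimus are covered throughout, including CNI-group patients who took MPA in the run-in.
- That outcome follow-up is cut off at 30 days. Section 8.2 follows a reported pregnancy to outcome without a limit.
- That the SAE window runs from the last dose. It runs from the end of participation.
- That only the CNI-free arm is affected. MPA was possible in both arms during the run-in.
- That partner wording exists nowhere. Section 8.2 ends in a redaction, probably contact details, and the pregnancy form and consent form are outside the two documents.

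It is also fair to say that the six-week and 90-day figures are contraception recommendations. Treating them as the period of concern is an interpretation, though the teratogenicity warning is the reason the protocol gives for them.

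**Conclusion.** The point holds in a limited form. Section 8.2 states a rule narrower than the precautions elsewhere in the same protocol. Under every definition of study drug it leaves out patients who conceive after study treatment ends but inside the contraception periods, and it leaves out partners of male patients altogether. The status of a patient off everolimus but on MPA is ambiguous.

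The size is 0 days of cover after study drug, against 42 and 90 days in section 6.5.1 and three months in inclusion criterion 5. The documents give no expected number of pregnancies, so the statement is that cases could be missed, not that they would be. The conclusion assumes that the redacted end of section 8.2 contains no further reporting scope. It has no bearing on the GFR comparison or any other efficacy analysis. It should be corrected because the safety gain is real and the change is cheap.

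**What to change.** Reword section 8.2 so that the 24-hour report and outcome follow-up apply to any pregnancy in a patient, or, with her consent, in the female partner of a male patient, where conception falls during protocol treatment with everolimus or MPA or within the protocol's own post-treatment contraception period. Three details need stating:

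- MPA counts for this rule, whatever study drug means elsewhere.
- The post-treatment period is counted from the last dose under the protocol regimen or from the end of study participation. Section 7.1 leaves later immunosuppression to the investigator, so a rule running until either drug finally stops could bind the sponsor indefinitely for patients who remain on these drugs.
- Section 6.5.1 gives a post-treatment period for MPA only, while inclusion criterion 5 gives women a different one tied to stopping the study. These passages must be reconciled before section 8.2 can refer to them. This review does not choose between them.

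The cost is protocol wording, a check of the pregnancy form, partner consent wording if none exists, and a few more reports and partner contacts.
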